7.3. Pharmacokinetic Measurements

Blood samples for assessment of plasma PK parameters for KZR-261 will be collected according to the Schedule of Events ([Appendix A](#)).

7.4. Exploratory Assessments

Samples for assessment of pharmacodynamic and other exploratory biomarkers will be collected during Cycles 1 and 2 from all subjects according to the Schedule of Events ([Appendix A](#)).

7.4.1. Pharmacodynamic and Biomarker Measurements

Whole blood samples will be collected for pharmacodynamic analyses according to the Schedule of Events ([Appendix A](#) and [Appendix B](#)). Pharmacodynamic analyses may include the monitoring of circulating proteins and/or proteins expressed in peripheral blood mononuclear cells.

Whole blood and tumor biopsy samples will be collected according to the Schedule of Events ([Appendix A](#) and [Appendix B](#)) to study circulating and tumor-derived biomarkers of drug activity, such as can be found in the DNA, RNA, and protein components of these samples. RNA-based biomarkers of gene expression may be particularly relevant. Selection of the tumor types targeted for the expansion cohorts was guided, in part, by an analysis of gene modules (eg, modules encoding Sec61 clients, ribosomal proteins, and constituents of Golgi vesicles) whose expression is both associated with sensitivity to Sec61 inhibition in vitro and found to be frequently perturbed in the selected tumor types. Pre-treatment tumor biopsies will be evaluated for expression of these gene modules, and the results will be correlated with KZR-261 response in an exploratory fashion. In subjects for whom both an on-treatment and baseline sample are available, a paired analysis of changes in the expression of these modules will be performed to better understand KZR-261's mechanism of action.

Additional information regarding sample collection and handling will be outlined in the Laboratory Manual.

7.5. Sample Management/Future Research

All samples will be coded with the subject number. Samples and any data generated can be linked back to the subject as detailed in [Section 4.1.1](#).

Samples collected for future research may be retained by the Sponsor or its designate for up to 5 years after study completion or as permitted by the applicable laws and regulations in the relevant country in which the study is conducted. Additional consent for storage of samples will be requested as a separate approval line on the ICF. Remaining de-identified unused clinical samples (blood/urine) will be retained by the Sponsor and used for the Sponsor's future research,

including, but not limited to, the evaluation of additional targets for novel therapeutic agents and to identify biomarkers for response and/or safety.

If additional written consent is not provided, any remaining biological samples will be destroyed by the Sponsor or its designate following study completion.

8. STUDY DISCONTINUATION

8.1. Stopping Rules for Safety

8.1.1. Study Stopping Rules

If any of the following events occur, the accumulated safety data will be reviewed by the SRC.

- Death of any subject due to an AE, unless the Grade 5 event is a complication of disease progression or intercurrent illness.
- Unexpected life-threatening event in 2 subjects, unless due to a complication of disease progression or intercurrent illness.
- Any event that contraindicates further enrollment of additional subjects as assessed by either the SRC or a regulatory authority.

In Part 2, the study will be halted if there is one Grade 5 or two Grade 4 AEs in different subjects considered at least possibly related to KZR-261. Exceptions include asymptomatic Grade 4 laboratory abnormalities (eg, neutropenia) that resolve either with or without routine supportive care measures and without sequelae.

Based on its review of any of the aforementioned scenarios, the SRC will have the ability to recommend the study be continued as is, continued with modification, or discontinued.

Modifications could include implementation of additional monitoring measures or a reduction of KZR-261 dose.

If any of these scenarios occurs, a formal safety analysis will be conducted, and the findings will be submitted to the IND for FDA review prior to enrolling additional subjects.

8.1.2. Individual Subject Stopping Rules

If any of the following events occur in an individual subject, administration of study drug should be held until a review of the accumulated safety data is undertaken by the Medical Monitor.

- Any scenario that fulfills criteria for Study Stopping Rules (per [Section 8.1.1](#)).
- Any scenario that, in the opinion of the Investigator or Medical Monitor contraindicates further dosing (eg, acute phase-like systemic drug reaction).

After such a review, the Medical Monitor in conjunction with the Investigator may recommend the subject resume dosing, including consideration for any prophylactic interventions (as per [Section 6.1.1](#)), or discontinue dosing. Alternatively, the Medical Monitor may request that the SRC review all accumulated safety data prior to issuing a recommendation whether to resume or discontinue dosing.

If any of the following events occur, administration of study drug to an individual subject should be discontinued:

- Intolerable toxicity unresponsive to appropriate supportive interventions
- Requirement for more than two dose reductions, or missed one entire treatment cycle
- PD

- Voluntary withdrawal by the subject from the study
- Requirement for a prohibited medication without a suitable alternative (including non-protocol anticancer therapy)
- DLT in Part 1, Cycle 1
- Pregnancy
- Physician's decision
- Closure of the study by the Sponsor ([Section 8.3.2](#)).

Subjects discontinuing study treatment must complete EOT assessments, particularly safety evaluations. The primary reason for study treatment discontinuation will be identified and recorded on the appropriate eCRF, along with the date of discontinuation.

8.2. Early Withdrawal of Subjects from Study

In accordance with applicable regulations, a subject has the right to withdraw from the study, at any time and for any reason, without prejudice to future medical care.

Subjects must be withdrawn from the study for any of the following reasons:

- Subject request/withdraw consent for any reason

Subjects may be withdrawn from the study for the occurrence of any of the following reasons:

- Use of non-permitted concurrent therapy
- Non-compliance with the study drug or study schedule
- Lost to follow-up
- Occurrence of AEs not compatible with the continuation of subject participation in the study, in the Investigator's or Sponsor's opinion, or unacceptable to the subject to continue
- Investigator request
- Sponsor request

The reason(s) for study withdrawal, if available, will be documented in the eCRF. If a subject withdraws consent, all samples obtained will be retained for analysis unless the subject confirms in writing that he or she wishes the samples to be discarded.

Reasonable efforts should be made to contact subjects who are lost to follow-up (defined as at least 3 unsuccessful contact attempts including 1 certified mail attempt). These efforts must be documented.

8.3. End of Treatment and End of Study

8.3.1. End of Treatment (or Early Withdrawal) Visit

The EOT / Early Withdrawal Visit will take place as soon as possible after permanent treatment discontinuation and prior to initiation of follow-on anticancer therapy ([Appendix B](#)). The following procedures will be performed at the EOT / Early Withdrawal Visit:

- Record any AEs that have occurred since the last visit and any changes in concomitant medication
- Record vital signs
- Record any clinically significant changes from baseline in physical examination as AEs
- Collect samples for hematology, clinical chemistry, and urinalysis.
- Perform assessments of response, if the subject stops study treatment for reasons other than PD and the last response assessment was performed >4 weeks before the EOT visit.

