7.2.10. Response Assessments

Assessments of response and progression will occur in accordance with RECIST v1.1 ([Eisenhauer et al., 2009](#)) at timepoints shown in the Schedule of Events ([Appendix A](#) and [Appendix B](#)). Subjects with mCRPC will be assessed per PCWG3 guidelines ([Scher et al., 2016](#)).

All subjects must have contrast-enhanced imaging studies of chest, abdomen, and pelvis as well as other areas of suspected disease within 28 days prior to their first dose of study treatment. The preferred imaging modality is contrast-enhanced computed tomography (CT). In subjects for whom IV contrast for CT is contraindicated, perform contrast-enhanced magnetic resonance imaging (MRI) scanning of the aforementioned anatomic regions with non-contrast enhanced CT of the chest. Subjects known to have fluorodeoxyglucose (FDG)-avid tumors are required to undergo positron emission tomography (PET) scanning along with the CT scan at Screening. Subjects whose tumors demonstrate FDG update at Screening should undergo follow-up PET scanning post-Cycle 6, post-Cycle 12, and every 6 cycles thereafter (see below). Subjects with skin, subcutaneous or lymph node metastases may also have evaluations of measurable lesions (including measurements, with a ruler or calipers) by means of physical examination.

Subjects with mCRPC must have a baseline PSA and bone scan in addition to the aforementioned imaging studies. (Note: A rising PSA as the sole indicator of disease activity will not lead to a determination of disease progression.) On-treatment bone scans will be performed at the same time points as CT/MRI scans. As a rule, the same imaging modality (ie, CT or MRI or combined CT/PET scans) should be used for all scheduled tumor assessments and measurements.

Imaging studies should be repeated prior to Cycle 3 (ie, end of Cycle 2) and every 2 cycles thereafter (ie, end of Cycles 4, 6, 8, etc). There is a 7-day window for imaging procedures to allow time for availability of results prior to the next cycle. If an imaging procedure must be scheduled to occur outside the 7-day window, this should be discussed with the Medical Monitor for approval prior to the procedure.

Response assessments, including imaging studies, are to be performed at the EOT visit, if PD has not already been established and the last response assessment was conducted >4 weeks prior to EOT.

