Subjects who discontinue study treatment for reasons other than PD will be contacted by telephone approximately every 90 days for 12 months after last study treatment for evidence of PD, collection of information about subsequent anti-tumor therapy, and assessment of survival status. Subjects who discontinue study treatment for PD will be contacted by telephone approximately every 90 days for 12 months after last study treatment for assessment of survival status.

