- ^j Imaging should be repeated prior to Cycle 3, prior to Cycle 5 (ie, end of Cycle 4) and every 2 cycles thereafter (ie, end of Cycles 4, 6, 8 etc.). There is a 7-day window around imaging procedures to allow time for result availability prior to the next cycle. If an imaging procedure must be scheduled to occur outside the 7-day window allowance, this should be discussed with the Medical Monitor for approval prior to the procedure. Imaging should be repeated at EOT if the last response assessment was >4 weeks prior. Tumors will be measured according to RECIST v1.1. Subjects with mCRPC will be assessed per PCWG3 guidelines. All subjects with mCRPC will have bone scans at the same time points as the imaging procedures. Subjects with skin, subcutaneous, or lymph node metastases may also have tumor evaluations (including measurements, with a ruler or calipers) by means of physical examination.
- ^k Day 28 assessments of the prior cycle may be combined with Day 1 of the next cycle. Whenever possible, these evaluations should be referred to as the End of Cycle evaluation (for the earlier cycle) as opposed to the beginning of cycle evaluation for the subsequent cycle.
- ^l Subsequent to discontinuation of study treatment, subjects will have an EOT visit as soon as possible following their last KZR-261 dose and prior to initiation of follow-on anticancer therapy. Safety follow-up by telephone will occur approximately 30 days after the subject's last dose of study treatment. If AEs have not resolved at that time, additional safety follow-ups will occur approximately every 30 days until AE resolution or until, in the opinion of the Investigator, the event is stabilized or determined to be chronic.
If a subject attending a Day 28 or Day 1 visit meets criteria for EOT, the EOT visit assessments should be conducted instead of Day 28/Day 1 assessments.

- ^m Subjects who discontinue study treatment for reasons other than PD will be contacted by telephone approximately every 90 days for 12 months after last study treatment for evidence of PD, collection of information about subsequent anti-tumor therapy, and assessment of survival status. Subjects who discontinue study treatment for PD will be contacted by telephone approximately every 90 days for 12 months after last study treatment for assessment of survival status.

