### 13.1. Disease Response Criteria

Evaluation of response and disease progression will be made by the Investigator according to RECIST v1.1 ([Eisenhauer et al., 2009](#)) guidelines except for mCRPC which will follow the PCWG3 modified RECIST v1.1 guidelines ([Scher et al., 2016](#)).

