### **13.2.3. Progression-Free Survival (PFS)**

PFS is defined as the date of initiation of KZR-261 until the date of documented PD or death from any cause, whichever occurs first.

$$PFS \text{ (weeks)} = \frac{([Date \text{ of } PD \text{ or } Death - Date \text{ of } First \text{ Dose} \text{ of } KZR - 261] + 1)}{7}$$

For subjects who have neither progressed nor died, PFS will be censored at the date of the last evaluable disease assessment. The median PFS will be estimated using Kaplan-Meier methods and summarized.

Progression-Free Survival at 4 months (PFS4) is defined as the percentage of subjects alive and progression-free at 4 months (ie, 17 weeks) after the initiation of study treatment. The PFS4 responders will be summarized using frequencies and percentages. Similar to analysis of ORR, two-sided 90% CIs for PFS4 responders using the Clopper-Pearson approach will be calculated.

Progression-Free Survival at 6 months (PFS6) is defined as the percentage of subjects alive and progression-free at 6 months (ie, 26 weeks) after the initiation of study treatment. The PFS6 responders will be summarized using frequencies and percentages. Similar to analysis of ORR, two-sided 90% CIs for PFS6 responders using the Clopper-Pearson approach will be calculated.

Separate Kaplan-Meier plots for subjects enrolled to Parts 1, 2A, and 2B will be provided.

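### The end-of-treatment response assessment has three different conditions; under Section 8.3.1, a stop for PD without RECIST/PCWG3 PD may reach PFS only at death, or be censored

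*Protocol*

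**What the plan says.** Three places in the protocol set the condition for the EOT response assessment.

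- Section 8.3.1, the list of EOT procedures: assess "if the subject stops study treatment for reasons other than PD and the last response assessment was performed >4 weeks before the EOT visit".
- Section 7.2.10, the response-assessment section: assess "if PD has not already been established and the last response assessment was conducted >4 weeks prior to EOT".
- Appendix B, footnote j, repeated in SAP Appendix B: "Imaging should be repeated at EOT if the last response assessment was >4 weeks prior".

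Section 8.1.2 lists PD and physician's decision as separate reasons to stop, without defining PD there, and adds: "The primary reason for study treatment discontinuation will be identified and recorded on the appropriate eCRF". After that the recorded reason decides the follow-up. Section 7.2.10 states: "Subjects who discontinue study treatment for PD will be contacted by telephone approximately every 90 days". The only purpose it gives for those calls is survival, so these subjects are not asked about progression again. Subjects stopped for any other reason are contacted for evidence of PD.

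On the analysis side, SAP 13.1 states: "Evaluation of response and disease progression will be made by the Investigator according to RECIST v1.1", with the PCWG3 modification for mCRPC. SAP 13.2.3 states: "PFS is defined as the date of initiation of KZR-261 until the date of documented PD or death from any cause". Subjects with neither event are censored at the last evaluable disease assessment. SAP 13 runs every efficacy analysis on the Response Evaluable Population, which SAP 6.2 limits to subjects with at least one post-baseline response assessment.

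**The concern.** The three conditions look at different things: the reason written on the form, whether PD has been established, or neither. They part for a subject whom the investigator stops for clinical progression between scans, with PD recorded as the reason and no RECIST or PCWG3 progression on file. Sections 7.2.10 and Appendix B ask for an assessment once 4 weeks have passed; Section 8.3.1 does not. Survival-only contact follows, so nothing later in the schedule would document the progression.

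If such a stop is not counted as documented PD, the subject is censored at a scan taken before the progression, or has an event only at a later death. That censoring is informative, and it favours PFS, PFS4 and PFS6. A subject stopped this way before the end of Cycle 2 has no post-baseline assessment and drops out of PFS, ORR and CBR.

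**Working it through.** The documents give no figure for this, so there is none to reproduce. The check compares the wordings and then sizes the difference under stated assumptions.

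**1. The three conditions side by side**

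| Subject at EOT | 8.3.1 | 7.2.10 | Appendix B, note j |
|---|---|---|---|
| Stopped for PD, RECIST/PCWG3 PD established, last assessment >4 weeks ago | no | no | yes |
| Stopped for PD, PD not established, >4 weeks ago | **no** | **yes** | **yes** |
| Stopped for another reason, PD not established, >4 weeks ago | yes | yes | yes |
| Last assessment within 4 weeks | no | no | no |

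The second row is the one that matters for PFS. In the last row no wording requires a scan, so aligning the wordings does not help those subjects.

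**2. What happens to the second-row subject under 8.3.1**

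No EOT assessment is made and no later question about PD is asked. The possible PFS entries are:
- an event on the stop date, if an investigator-recorded PD counts as documented;
- an event at a later death;
- censoring at the last evaluable assessment.

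The SAP does not say which applies.

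**3. Assumptions for the size**

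From the documents: response assessments every 2 cycles, that is every 8 weeks, and a 17-week landmark for PFS4. Assumed: exponential time to progression with median 4 months (17.39 weeks), so λ = ln 2 / 17.39 = 0.0399 per week; 10% or 20% of progressions clinical; median survival of 6 months after PD; deaths within 12 months counted as events; baseline imaging at the start of treatment.

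**4. How often the wordings can differ**

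- Share of clinical stops within 4 weeks of the previous scan: 1/(1 + e^(−4λ)) = 1/(1 + 0.853) = 54%. Here all three wordings agree.
- Share before the first on-study scan at week 8: 1 − e^(−8λ) = 1 − 0.727 = 27.3%.
- Share in the first 4 weeks, unscanned under every wording: 1 − e^(−4λ) = 14.7%.

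Under 8.3.1, 0.273 × 10% = 2.7% to 0.273 × 20% = 5.5% of subjects would leave the Response Evaluable Population. The part due to the choice of section is (27.3 − 14.7)% = 12.6% of clinical stops, or 1.3% to 2.5% of subjects.

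**5. Kaplan-Meier PFS at 17 weeks (simulated)**

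| Rule | 10% clinical | 20% clinical |
|---|---|---|
| 8.3.1: clinical stops unscanned | 56.0% | 59.3% |
| 7.2.10 / Appendix B: scanned if >4 weeks | 54.4% | 56.1% |
| Stop date counted as the event | 52.5% | 52.3% |

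The bottom row can be checked by hand. Radiographic PD is seen at scans, so week-17 PFS is 2^(−16/17.39) = 52.9% for those subjects and 2^(−17/17.39) = 50.8% for clinical stops. Then 0.9 × 52.9 + 0.1 × 50.8 = 52.7%, and 0.8 × 52.9 + 0.2 × 50.8 = 52.5%, which agree to about 0.2 point.

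- Effect of the choice of section: 56.0 − 54.4 = 1.6 points and 59.3 − 56.1 = 3.2 points (up to 3.3 with simulation noise).
- Full gap against counting the stop date: 56.0 − 52.5 = 3.5 points and 59.3 − 52.3 = 7.0 points.

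Just after 26 weeks the full gap is 41.6 − 38.0 = 3.6 and 44.9 − 37.7 = 7.2 points. With a 6-month median it is about 3 to 6 points. With medians of 8 or 16 weeks and 10% to 30% clinical progression it is about 3 to 12 points at week 17.

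**6. The SAP's own PFS4 estimator**

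SAP 13.2.3 reports PFS4 as a simple percentage with an exact interval, not a Kaplan-Meier estimate. On that scale the section difference is about 1.1 points (10%) and 2.2 points (20%).

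**The case against.** A reader might infer that, under 8.3.1, such a progression never enters PFS as documented PD, and that PFS is therefore overstated by 3 to 7 points. The documents do not support that. It needs three things, none of which they settle.

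- *PD as a stopping reason must include progression outside RECIST/PCWG3.* SAP 13.1 and its subsections use PD as a response category under those criteria. If 8.1.2 means the same, a subject stopped for PD already has it established, and 8.3.1 and 7.2.10 largely coincide. Clinical deterioration could be recorded as physician's decision, which triggers both the 8.3.1 assessment (after 4 weeks) and follow-up for PD.
- *Documented PD must exclude an investigator-recorded date.* The term is undefined. Investigators judge progression, skin and nodal lesions may be measured by physical examination, and Appendix B collects disease/survival status at EOT.
- *Section 8.3.1 must prevail.* No precedence is stated. Section 8.3.1 itself cites Appendix B, Appendix A footnote q sends sites there for EOT evaluations, and the 8.3.1 list omits the ECG, slit-lamp, coagulation and ECOG items that Appendix B marks at EOT.

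The 3 to 7 points also overstate what the wording does, because more than half of the assumed clinical stops fall where all three rules agree. PFS is a secondary, descriptive endpoint, and the Part 2A futility decision uses CBR.

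These objections limit the claim but do not remove it. The conflict is in the text. The protocol recognises clinical progression on prior therapy in its uveal melanoma entry criteria, so on-study clinical progression is foreseeable. As written, a form entry and the section a site happens to read decide whether the progression can be documented.

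**Conclusion.** The point holds as a conflict between sections with a conditional effect on PFS. The three EOT conditions differ. A subject stopped for PD without RECIST/PCWG3 PD, last assessed more than 4 weeks earlier, is assessed under 7.2.10 and Appendix B but not under 8.3.1. That progression may then enter PFS late, at death, or be censored. If the stop comes before the first on-study scan, the subject may leave all efficacy analyses.

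The direction is towards more favourable PFS. Under the illustrative assumptions, about 1.6 to 3.3 Kaplan-Meier points at 17 weeks are due to the choice of section. The full gap of about 3 to 7 points also includes stops within 4 weeks of a scan, which only an SAP rule can address. Everything scales with the clinical-progression rate, which has no source in the documents. It should be corrected, since the remedy is small, but it does not threaten the primary safety objectives.

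**What to change.** - Use one EOT condition in Protocol 8.3.1, Protocol 7.2.10 and Appendix B footnote j of both documents. Base it on whether RECIST/PCWG3 PD has been established, not on the recorded stopping reason. Editing 8.3.1 alone would leave footnote j different.
- In SAP 13.2.3, define documented PD and state whether a stop for PD without RECIST/PCWG3 PD is a PFS event on that date or is censored. This is the only remedy for stops within 4 weeks of a scan.
- Add a sensitivity analysis under the other rule that also includes such subjects with no post-baseline assessment.

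The cost is a sentence in each place and one extra analysis. Two of the three places already require the assessment. Reported PFS may be slightly less favourable.
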